6.3 Initial Clinical Evaluation

- 1. Complete history and physical exam.
- 2. CBC with differential and platelet count (CBCDP); within 14 days prior to start of treatment
- Serum chemistry profile to include: comprehensive panel (Na, K, Cl, CO2, BUN, Cr, Gluc, AST/SGOT, ALT/SGPT, Alk Phos, T.bili, Alb, Ca, Total Protein), serum magnesium; within 14 days prior to start of treatment.
- 4. Urine dip (in clinic or lab)
- 5. TSH, free T4; within 14 days prior to start of treatment
- 6. Pregnancy test (serum or urine Beta-HCG) in women of childbearing potential; within 3 days prior to start of treatment.
- 7. Radiologic imaging of the areas involved with recurrent/metastatic disease, such as the neck, chest, or other areas if needed because of the location of the metastatic disease; within 28 days prior to treatment.

7. STUDY PLAN

7.1. Study overview

The patients will receive 5 mg Axitinib twice a day. Dose escalation is planned at 2 weeks (to 7 mg BID) and at 3 weeks (to 10 mg BID), in the absence of toxicities grade 2 or greater. Dose escalation may be resumed at next visit if all toxicities have diminished to grade 1 or less (see

below) since last follow-up. Each patient will be seen in clinic at 2, 4, 8 weeks after initiation of treatment and at monthly intervals thereafter, unless more frequent follow-up is clinically indicated.

During follow-up visits, we will assess the toxicities, including checking vital signs, review of systems, physical exam and CBCDP, comprehensive metabolic panel, test for proteinuria. TSH should be checked within 14 days of cycle 1, day 1 then should be done every 2 weeks for two assessments. Following completion of these assessments, TSH should be checked following the completion of even numbered cycles of chemotherapy.

Telephone call to the patient must be made by a study staff member (licensed RN or MD) at 1 and 3 weeks. During these calls, toxicity assessment will be conducted, per patient report, and toxicity management advice given, including initiation or titration of anti-hypertensive treatment. During the Week 3 call, if toxicities are grade 1 or less since last follow-up, dose escalation to 10 mg BID will be made. Dose escalation may be resumed at least 1 week later if all toxicities have diminished to grade 1 or less (see below), and measures have been taken to reasonably prevent recurrence of these toxicities with the higher dose since last follow-up.

The response to treatment will be assessed clinically at each visit, as well as by appropriate radiologic imaging, starting at 8 weeks +/- 2 weeks and then at 8-week intervals, +/- 2 weeks. Tumor response to therapy will be interpreted by Choi Criteria with interpretation performed by UMCC Tumor Response and Assessment Core. Patients will be taken off trial for significant side effects, per patient preference, or for noncompliance with treatment plan. Beyond progression, survival will be assessed every 12 weeks. Patients will also be followed for 28 days after cessation of study participation for safety monitoring. Patients with confirmed progressive disease who, in the investigator's opinion, continue to receive benefit from Axitinib treatment and who meet the criteria for treatment may continue to receive treatment as described in Section 8.3. Axitinib should be discontinued if there is further evidence of progression defined as an additional 10% or greater increase in tumor burden volume from time of initial progression (including all target lesions and new measurable lesions).

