6.2. Trial procedures

During treatment on this protocol, all patients will be followed and monitored as follows:

Table 6. Trial Procedures.

		Cycle						Following	Following completion	al ¹¹
D 1	D	l,	1		2	4	0	each	of even	viv
Required	Pre-	Day		2	3	4	8	cycle thru	numbered	Sur
studies	therapy ¹²		week	weeks	weeks	weeks	weeks	12 cycles ¹	cycles	01
Clinic visit	X	X		X		X	X	X	X	
H&P	X	X^{10}		Х		X	X	Х	Х	
Vital signs and PS	Х	Х		Х		Х	Х	Х	Х	
PTT, PT, INR	Х									
CBC, Diff, platelets	Х	X ⁹		Х		Х	Х	Х	Х	
Comprehensive Panel, Mg ²	X ³	X ⁹		Х		Х	Х	Х	Х	
Urine dip ³	Х					Х	Х	Х	Х	
TSH, free T4 ⁴	Х	X ^{9,}		Х		Х			Х	
Clinical										
toxicity				Х		Х	Х	Х	Х	
assessment										
Radiologic										
imaging for	v						v		\mathbf{v}	
tumor	Λ						Λ		Λ	
measurement ⁵										
Pregnancy Test ⁶		X ⁹								
Informed	v									
Consent	Λ									
Planned dose				v	v					
escalation ⁷				Λ	Λ					
Telephone										
assessment of			Х		Х					
toxicities ⁸										
Survival										v
Monitoring										Λ

- 1- Following completion of 12 cycles, assessments will be obtained every 8 weeks.
- 2- Comprehensive Panel includes Basic Panel (Na, K, Cl, CO2, BUN, Cr, Gluc), AST/SGOT, ALT/SGPT, Alk Phos, T.bili, Alb, Ca, Total Protein. Also will obtain magnesium.
- 3- Urine dipstick may be done in clinic or lab.
- 4- Serum or plasma Thyroid Function Tests (Free T4 and TSH) should be performed within 14 days of starting treatment. Subsequently, TSH should be done every 2 weeks X 2, then following completion of even numbered cycles of chemotherapy.

- 5- Radiologic imaging of the areas involved with recurrent/metastatic disease, such as the neck, chest, or other areas if needed because of the location of the metastatic disease; baseline within 28 days prior to treatment. On study assessments, may be within +/- 2 weeks. Imaging will be interpreted by Choi Criteria, interpretation to be performed by centralized UMCC Tumor Response and Assessment Core (TRAC).
- 6- Pregnancy test (urine or serum) will be performed for women of childbearing age within 3 days before first dose of Axitinib and if clinical concern for pregnancy arises.
- 7- Dose escalation is planned at 2 weeks (to 7 mg BID) and 3 weeks (to 10 mg BID), in the absence of toxicities grade 2 or greater. Dose escalation may be resumed after 1 week if all toxicities have diminished to grade 1 or less (see below), and measures have been taken to reasonably prevent recurrence of these toxicities with the higher dose.

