- 8- Telephone call to the patient must be made by a study staff member (RN or MD with a current nursing/medical license) at 1 and 3 weeks. During these calls, toxicity assessment will be conducted, per patient report, and toxicity management advice given, including initiation or titration of anti-hypertensive treatment. During the Week 3 call, if toxicities are grade 1 or less dose escalation to 10 mg BID will be made.
- 9- All baseline labs are required within 14 days of starting treatment (Cycle 1, Day 1).
- 10-H&P not required on Cycle 1, Day 1 if performed for screening within 72 hours
- 11- Survival assessment can be done by phone and will be performed once every three months (+/- 1 month)
- 12-Labs are eligible for screening if obtained within the past 28 days

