8.2.3. Dose escalations

Dose escalation is planned at 2 weeks (to 7 mg BID) and at 3 weeks (to 10 mg BID), in the absence of toxicities grade 2 or greater since last follow-up. Dose escalation may be resumed after at least 1 week if all toxicities have diminished to grade 1 or less since last follow-up. Each patient will be seen in clinic at 2, 4, 8 weeks after initiation of treatment and at monthly intervals thereafter, unless more frequent follow-up is clinically indicated. Telephone call to the patient must be made by a study staff member (a doctor or a nurse) at 1 and 3 weeks, +/- 3 days. During these calls, toxicity assessment will be conducted, per patient report, and toxicity management advice given. During the Week 3 call, if toxicities are grade 1 or less since last follow-up, Axitinib dose escalation to 10 mg BID will be made. Dose escalation up to 10 mg po BID may be resumed after at least 1 week if all toxicities have diminished to grade 1 or less (see below), and measures have been taken to reasonably prevent recurrence of these toxicities with the higher dose. The contents of each planned and patient-initiated phone called will be recorded in patient's study record.

If a patient has a dose reduction for study drug related toxicity, the dose may be considered for re-escalation in patients who tolerate the lower dose without toxicities above Grade 1 for at least 1 week, and measures have been taken to reasonably prevent recurrence of these toxicities with the higher dose.

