8.2.4.3. Axitinib Dose Reduction for Proteinuria

At documentation of >1+ proteinuria by dipstick, patients should have a 24-hour urine collection for total protein. Axitinib dosing may continue while waiting for test results.

If ≤ 2 g proteinuria/24 hours is reported, treatment with Axitinib may continue without dose reduction.

If >2 g proteinuria/24 hours is reported, treatment with Axitinib should be interrupted. A twenty-four hour urine collection for total protein and creatinine clearance should be performed weekly until results show \leq 2 g proteinuria/24 hours, at which time treatment with Axitinib may be restarted at one lower dose level. Patients, once restarted on Axitinib, will have every-2-weeks monitoring for proteinuria by semiquantitative testing (e.g., dipstick) as long as the proteinuria reading is higher than 1+. The 24-hour urine collection to monitor the degree of proteinuria should be repeated every 4 weeks until it has decreased to <500 mg/24 hours. If recurrent >2 g proteinuria/24 hours is reported, treatment with Axitinib should be interrupted again. Twenty-four hour urine collection for total protein and creatinine clearance should be performed every 2 weeks until results show \leq 2 g proteinuria/24 hours, at which time treatment with Axitinib may be restarted at one lower dose level. If a patient requires dose reduction below 2 mg BID, stop trial participation.

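### Table 6 omits the week 2 urine dipstick that section 7.1 calls for, so a site following the table makes both dose escalations without an on-treatment urine result

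*Combined protocol and SAP*

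**What the plan says.** Section 7.1 (Study overview) schedules clinic visits at 2, 4 and 8 weeks and then monthly. Among the assessments at follow-up visits it lists "comprehensive metabolic panel, test for proteinuria". Nothing there exempts the week 2 visit.

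Table 6 (section 6.2) leaves the urine dip cell blank at week 2. The footnote attached to that row concerns location only: "Urine dipstick may be done in clinic or lab".

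Footnote 7 sets the dose steps: "Dose escalation is planned at 2 weeks (to 7 mg BID) and 3 weeks (to 10 mg BID), in the absence of toxicities" of grade 2 or greater. Section 8.2.3 words the condition as "in the absence of toxicities grade 2 or greater since last follow-up". The week 3 step is decided in a telephone call, for which footnote 8 says: "During these calls, toxicity assessment will be conducted, per patient report".

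Section 8.2.4.3 gives proteinuria its own rule, which starts from a dipstick: "At documentation of >1+ proteinuria by dipstick, patients should have a 24-hour urine collection for total protein".

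**The concern.** The text and the schedule table disagree about one safety test, at the visit where the first escalation is decided. A study coordinator working from Table 6 would not do the test.

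Proteinuria is a laboratory finding. A dipstick is the trigger for the rule in 8.2.4.3, and a patient's report by telephone cannot replace it. If Table 6 governs, the dose can double from 5 to 10 mg BID while the toxicity condition remains unverified for proteinuria. Section 11 names proteinuria for special attention. Inclusion criterion 3 also admits patients with a baseline dipstick of 2+ or more if their 24-hour protein is below 2 g, so some may start close to the level above which 8.2.4.3 interrupts dosing.

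**Working it through.** **1. Is the blank cell real?** Table 6 was read by column position. Rows that section 7.1 describes independently were used to check the alignment.

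| Table 6 row | Marked at | Agrees with 7.1? |
|---|---|---|
| Clinic visit | pre-therapy, day 1, weeks 2, 4, 8, later | yes (weeks 2, 4, 8) |
| Telephone assessment | weeks 1, 3 | yes |
| Planned escalation | weeks 2, 3 | yes |
| TSH, free T4 | pre-therapy, day 1, weeks 2, 4, even cycles | yes |
| CBC | pre-therapy, day 1, weeks 2, 4, 8, later | yes |
| Clinical toxicity assessment | weeks 2, 4, 8, later | yes |
| Urine dip | pre-therapy, weeks 4, 8, later | **no: week 2 missing** |

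The other rows line up, so the blank is not a column shift from text extraction. Week 2 is the only clinic visit after day 1 without a urine dip.

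**2. On-treatment urine results available at the planned steps.** Under Table 6 there are 0 before the 7 mg step (week 2) and 0 before the 10 mg step (week 3). Under 7.1 there is 1, from the week 2 visit.

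**3. Exposure before the first on-treatment dipstick, if Table 6 is followed.** With both steps on schedule:
- at 7 mg BID: 21 − 14 = 7 days
- at 10 mg BID: 28 − 21 = 7 days

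**4. Age of the latest result, if Table 6 is followed.** Section 6.3 gives the urine dip no window of its own, so two readings are possible.
- Footnote 9, "All baseline labs are required within 14 days of starting treatment": up to 14 + 14 = 28 days at the 7 mg step and 14 + 21 = 35 days at the 10 mg step.
- Footnote 12, "Labs are eligible for screening if obtained within the past 28 days", taken as before treatment start: up to 28 + 14 = 42 and 28 + 21 = 49 days.

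On either reading the result predates all axitinib.

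**5. How common is the event?** Table 3, urine protein, maximum grade, N = 476: grade 2 in 88, grade 3 in 14, grade 4 in 0.
- Grade 2 or 3: (88 + 14)/476 = 102/476 = 21.4% (exact 95% CI 17.8% to 25.4%). Applied to 37 patients, 37 × 0.214 ≈ 8.
- Grade 3: 14/476 = 2.9% (exact 95% CI 1.6% to 4.9%).

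These are rates at any time on treatment. The documents give no onset times, so the share arising by week 2 or 3 is unknown and the figure of about 8 is an indication of scale only.

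**The case against.** The strongest reply is that 7.1 is operative text and already requires the test, so Table 6 merely lacks a mark and harm follows only if staff prefer the table. That is correct, and the conclusion is conditional on it. It does not remove the conflict, because the protocol does not say which of the two governs.

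A second reply is that the consequence is limited. Week 2 has vital signs, a comprehensive panel and a toxicity assessment. Entry requires a dipstick below 2+ or 24-hour protein below 2 g. A dipstick follows at week 4 in any case. Section 8.2.4.3 lets dosing continue at 2 g/24 hours or less and while a collection is pending. All of this stands as a limit on severity. None of it supplies a urine result at the time of escalation.

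Third, the rates do not size the problem, and the age of a pre-treatment result is secondary because any such result predates the drug. Both points stand. The conclusion rests on neither.

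Fourth, the remedy is partial. Looking at the week 2 result again at week 3 brings no new data, and proteinuria first arising between those weeks is still found only at week 4. This also stands. The remedy nevertheless provides one on-treatment result where Table 6 provides none.

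**Conclusion.** The inconsistency is real and should be corrected. If Table 6 is followed, both planned escalations go ahead with no scheduled on-treatment urine result, and the grade 2 condition in 8.2.3 cannot be verified for proteinuria. The first dipstick on drug then comes after 7 days at 7 mg BID and 7 days at 10 mg BID.

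This assumes escalation on the planned dates; if a step slips to week 4 or later, the week 4 dipstick is available. It also assumes that no unscheduled test is done. The number of patients affected cannot be derived from the documents. The matter is one of safety monitoring: the primary endpoint, sample size and analysis are untouched.

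**What to change.** Mark the urine dip in the week 2 column of Table 6, to agree with 7.1. Add a clause to 8.2.3 stating that the week 2 dipstick result is reviewed before the 7 mg decision, and again before the 10 mg decision at the week 3 call. The thresholds in 8.2.4.3 stay as they are.

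The cost is one table cell, one clause, and one dipstick per patient at a visit that already takes place and where 7.1 already asks for the test.

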7.2 Study schema

Figure 5. Study schema

¹ Patients with confirmed progressive disease who, in the investigator's opinion, continue to receive benefit from Axitinib treatment and who meet the criteria for treatment may continue to receive treatment as per Section 8.3.

² Patients who do not complete at least one month of treatment nor undergo tumor-reimaging for reasons other than progression of disease will be considered non evaluable for the primary endpoint and will be replaced unless tumor progression is obvious by clinical exam. All patients who received at least 1 dose of Axitinib under this protocol will be included in the safety analysis

³Response will be assessed by Choi Criteria

⁴Survival assessment can be done by phone and will be performed once every three months (+/-1 month)

8. TREATMENT PLAN:

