8.2.4. Dose Interruption and Reductions

Adverse events and other symptoms will be graded according to the current Common Terminology for Adverse Events version 4.03 (CTCAE v4.03). This section contains management of adverse events except hypertension, hemoptysis and proteinuria which are discussed in subsequent sections.

Patients developing a treatment-related CTCAE Grade 1 or 2 adverse event will have their dose continued at the same dose level. Patients developing a treatment-related CTCAE Grade 3 or above adverse event will have dose reductions as described below.

Treatment delays due to drug-related toxicity > 2 weeks will result in discontinuation of treatment. Patients removed from treatment for intolerable toxicity will still be followed for survival.

The criteria for dose modification for study drug related adverse events is summarized Table 8 below.

Table 8. Criteria for Dose Modification for Axitinib Related Adverse Events other than Hypertension, Hemoptysis, or Proteinuria

Related Adverse Events	Intervention
Grade 1	Continue at same dose level
	May escalate dose per protocol
	Manage toxicities as medically necessary
Grade 2	Continue at same dose level
	Manage toxicities as medically necessary
Grade 3 nonhematologic	Decrease dose to one lower dose level
drug-related toxicity	Manage toxicities as medically necessary
	Treatment may be interrupted up to 2 weeks per investigator discretion
Grade 4 nonhematologic drug-related toxicity or Grade 4 hematologic toxicity*	Interrupt dosing (up to 2 weeks); re-start at one lower dose level as soon as improvement to CTCAE Grade 2. If patient requires dose reduction below 2 mg BID, discontinue trial participation. Manage toxicities as medically necessary
*Patients who develop grade 4 lymphopenia may continue study treatment without interruption.	

Guidelines for dose reductions for specific adverse events are provided in the following sections.

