13. STATISTICAL METHODS

13.1. Primary Objectives:

The primary aim of this study is to compare 6-month overall survival after treatment with Axitinib in patients with unresectable, recurrent or metastatic head and neck cancer to historical rates. Based on results in the literature, we assume a 6-month mortality rate of **50%** under current standard care in this patient population (11, 52). We will test whether survival after treatment with Axitinib is improved to 70% at 6-months compared to 50%.

Overall survival will be determined from the date of treatment initiation to date of death from any cause. For the primary endpoint, patients that are alive at 6 months following the initiation of study treatment will be considered successful. All other patients will be considered unsuccessful. Patients will be considered evaluable for the primary endpoint if they receive any dose of Axitinib.

13.2. Sample size justification:

We will enroll 37 additional patients for comparison of overall survival. Based on historical data, 6 month OS in heavily pretreated patients such as those included in this study is 50%. Thirtyseven patients will provide 80% power to detect a meaningful difference in proportion alive at 6months (70% vs 50% historically) with a type I error rate of 5%. For the primary endpoint of overall survival we anticipate no missing data and will test whether the proportion alive at 6 months is greater than the historical rate of 50% with an upper tailed test of binomial proportion.

Based on our prior experience at the University of Michigan, we anticipate accrual of approximately 4 patients every 5 months. With this rate of accrual, we can enroll 40 eligible patients in 50 months. With a minimum follow-up of 6 month for each patient, the study will complete in about 56 months.

13.3. Stopping rules for futility:

As we observed considerable evidence of activity in UMCC 2011.053, we plan no interim analysis for futility with data collected in the expansion cohort B. Formal analysis of efficacy will be performed at trial completion.

13.4. Analysis plan:

- To estimate survival rates.

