18. COMPLETION OF TREATMENT AND FOLLOW-UP

After completion of treatment on study patients will be followed for survival. Survival assessment can be done by phone and will be performed once every three months (+/- 1 month)

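### Section 7.2 footnote 2 and sections 13.1/14.1 define the primary-endpoint denominator differently; at the success threshold, one removed death reverses the result

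*Combined protocol and SAP*

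**What the plan says.** Two places define who counts for the primary endpoint, which is being alive 6 months after starting treatment.

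- **Sections 13.1 and 14.1**, in identical words: "Patients will be considered evaluable for the primary endpoint if they receive any dose of Axitinib". Patients alive at 6 months are successes, and "All other patients will be considered unsuccessful".
- **Section 7.2, footnote 2** singles out this group: "Patients who do not complete at least one month of treatment nor undergo tumor-reimaging for reasons other than progression of disease". Its consequence for the group is that they "will be considered non evaluable for the primary endpoint and will be replaced unless tumor progression is obvious by clinical exam". The footnote's next sentence uses receipt of at least one dose only to define the safety set.

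Other sections bear on whether the 6-month outcome is obtainable for patients who stop early. Section 13.2 states: "For the primary endpoint of overall survival we anticipate no missing data". Section 8.2.4 states: "Patients removed from treatment for intolerable toxicity will still be followed for survival". Section 18 states: "After completion of treatment on study patients will be followed for survival", and it allows the check to be made by telephone. Section 7.1 lists reasons for leaving that are not progression: "Patients will be taken off trial for significant side effects, per patient preference, or for noncompliance with treatment plan".

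Section 13.4 refers to 37 evaluable patients for the survival estimates without saying which definition applies.

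**The concern.** Both rules name the primary endpoint, so the footnote cannot be read as covering response only. It cannot be confined to patients who never started drug either, because it describes people who fail to complete a month of treatment.

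The footnote's conditions also do not fit the endpoint. Neither a month of treatment nor a repeat scan is needed to know whether someone is alive at 6 months, so applying the footnote discards outcomes that the protocol expects to have.

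What remains after that removal is a group selected on what happened after treatment began, and it would be tested against an unselected historical rate of 50%. If the removed patients do worse than the rest, the test is biased towards success. With two rules on paper, the denominator could also be settled after the outcomes are known. Even without any such intent, two analysts could each follow the protocol and reach opposite conclusions.

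**Working it through.** **Inputs.** From sections 13.1, 13.2 and 14.1: n = 37, null survival 0.50, alternative 0.70, one-sided binomial test at 5%, no missing data anticipated. The documents do not give the share of dosed patients that footnote 2 would remove, or their 6-month survival; both are assumed in step 4.

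**Step 1. Reproduce the design.** P(X ≥ r | n, p) = Σ C(n,k) p^k (1−p)^(n−k), summed over k from r to n.

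- P(X ≥ 23 | 37, 0.5) = 0.0939, above 5%.
- P(X ≥ 24 | 37, 0.5) = 0.0494, so success needs 24 or more alive.
- P(X ≥ 24 | 37, 0.7) = 0.8071, the stated 80% power.
- Normal approximation: n = [(1.645·√0.25 + 0.842·√0.21)/0.2]² = 36.5, rounded up to 37.

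The stated sample size is correct when every dosed patient counts.

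**Step 2. One patient under both rules.** Take a patient who dies in week 3 of toxicity or intercurrent illness, with no re-imaging and no progression. Under 13.1 and 14.1 this is a failure in the denominator. Under footnote 2 the patient leaves the denominator and another is enrolled.

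**Step 3. Effect at the threshold.** Suppose 24 of the 37 counted patients are alive (p = 0.0494, success). Restore the removed patients:

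| Removed patients restored | All-dosed result | One-sided p |
|---|---|---|
| 1 death | 24/38 | 0.0717 |
| 2 deaths | 24/39 | 0.0998 |
| 3 deaths | 24/40 | 0.1341 |
| 2 deaths, 1 survivor | 25/40 | 0.0769 |
| 1 death, 2 survivors | 26/40 | 0.0403 |

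The first four rows reverse the conclusion and the last does not.

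**Step 4. Type I error if the footnote is applied.** Let e be the share of dosed patients removed and q their 6-month survival. If true survival among all dosed patients is 50%, then 0.5 = (1−e)p + eq. Survival among those kept is therefore p = (0.5 − eq)/(1−e), and the type I error is P(X ≥ 24 | 37, p). For example, e = 0.05 and q = 0 give p = 0.5/0.95 = 0.526 and a type I error of 0.0917.

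| Removed share (assumed) | q = 0% | 20% | 40% | 50% | 60% |
|---|---|---|---|---|---|
| 5% | 9.2% | 7.2% | 5.6% | 4.9% | 4.3% |
| 7.5% | 12.4% | 8.8% | 6.0% | 4.9% | 4.0% |
| 15% | 28.4% | 15.7% | 7.6% | 4.9% | 3.1% |

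The error rises when q is below 50%, is unchanged at 50%, and falls above it.

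**The case against.** The statistical sections are not themselves ambiguous: 13.1 and 14.1 agree, and the contrary text is one footnote to a figure. A statistician working from sections 13 and 14 would use all dosed patients. That is true, but the footnote is protocol text, it governs enrolment and replacement, and no clause ranks it below section 13.

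The reversal is a borderline case. It needs exactly 24 of 37 counted patients alive, which has probability 0.0494 − 0.0235 = 2.6% if true survival among those counted is 50%, and 0.8071 − 0.6983 = 10.9% if it is 70%. With 25 of 37 counted alive, restoring one death gives 25/38 (p = 0.036) and success stands. This limits how often a single patient decides the trial.

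The 38-patient denominator arises only if the footnote has driven replacement and 13.1 then governs the analysis. Had 13.1 governed throughout, enrolment would have stopped at 37 dosed. The result would then be 23/37 (p = 0.094) if the replacement patient survived, or 24/37 (p = 0.049) if the replacement died. That is a fair distinction, but once a replacement has been made, 24/37 and 24/38 are the same data under the two written rules.

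The type I error figures rest on assumptions, and the group may be small. Progressors are kept, a patient must lack both a month of treatment and re-imaging, and people who leave by preference or for noncompliance are included. The predecessor trial (section 1.2) had 42 enrolled and 30 available for efficacy, but that was for another endpoint and without reasons, so it does not settle the share. The size of the bias is therefore unknown. Survival below 50% in the removed group is likely, because it contains early deaths without progression, but it is not established.

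**Conclusion.** The concern holds and should be fixed before analysis. The documents give two incompatible definitions of the denominator for the trial's only formal efficacy test, with no order of precedence. The sample size and power are right for the all-dosed rule; the fault lies in the footnote.

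The contradiction and the exact p-values rest on no assumption beyond the stated design. The reversal applies only to results at the threshold. The type I error range, from 3.1% to 28.4%, is illustrative because both the removed share and its survival are assumed. It shows that the nominal 5% is not assured under the footnote; it does not estimate the error the trial would actually have.

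**What to change.** - Delete the first sentence of footnote 2 in section 7.2 and keep its second sentence on the safety analysis. If the rule is wanted for imaging, confine it to the radiologic response endpoints.
- Let sections 13.1 and 14.1 govern the primary endpoint, with no replacement of dosed patients. Defining the 37 as dosed patients also means that someone registered but never treated does not use up a place.
- State in section 13.4 that the 37 evaluable patients for overall survival are the 37 dosed patients, and put the success threshold of 24 or more alive in the plan.
- If any dosed patient has already been replaced, analyse all dosed patients against the exact threshold for that number: 25 of 38 (alpha 0.0365), 26 of 39 (0.0266) or 26 of 40 (0.0403).
- An evaluable-only result may be kept as a labelled sensitivity analysis.

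A minor clarification while amending: section 13.2 projects 40 eligible patients in 50 months, while the sample size is 37. At 4 patients per 5 months (0.8 per month), 37 take 37/0.8 = 46.25 months. The text should align the two figures or say what the extra three are for.

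The cost is a wording amendment, with no added patients or visits. The observed 6-month survival may be somewhat less favourable than it would be with replacement.
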